2.6.1.3 Other secondary efficacy endpoints

Time to treatment failure (TTF) is defined as the time from date of randomization to an event of treatment failure define as BCR::ABL1 > 1% IS. The following events will constitute ‘treatment failure’ for analysis purpose, and are based on the ELN criteria 2020 defining failure of a second line treatment adapted to include discontinuation of randomized treatment as an event:

- BCR::ABL1 >1% IS at 48 weeks after initiation of therapy or no complete cytogenetic response at 48 weeks.
- Subject demonstrates new T315I mutation
- Subject shows lack or loss of response such as “Loss of CHR, CCyR or PCyR at any time after initiation of therapy OR confirmed loss of MMR”
- Progression to AP/BC

For subjects who have not reached treatment failure, their TTFs will be censored at the time of last study assessment (PCR, cytogenetic, hematologic or extramedullary) before the cut-off date.

TTF (in months) is calculated as: (date of treatment failure or censoring date (see [Section 2.6.2](#)) - date of randomization + 1)/30.4375.

Progression-Free-Survival (PFS) is defined as the time from the date of randomization to the earliest occurrence of documented disease progression to AP/BC or the date of death from any cause before the cut-off date. The time will be censored at the date of last study assessment (PCR, cytogenetic, hematologic or extramedullary) or last post-treatment follow-up for subjects without event.

PFS (in months) is calculated as: (date of disease progression/death or censoring date (see [Section 2.6.2](#)) - date of randomization + 1)/30.4375.

Overall survival (OS) is defined as the time from the date of randomization to the date of death. Subjects who are alive at the time of the analysis data cutoff date will be censored at the date of last contact (see [Section 2.1.1](#)) before the cut-off date. OS (in months) is calculated as: (date of death or censoring date (see [Section 2.6.2](#)) - date of randomization + 1)/30.4375.

2.6.2 Statistical hypothesis, model, and method of analysis

No statistical testing of secondary efficacy endpoints will be performed .

Molecular response at and by time points

- Molecular Response MMR rate at weeks 12, 24, 36, 72, 96 and 144
- MMR rate at week 48 for subjects with MMR at baseline
- Rate of MR4 and MR4.5 at weeks 12, 24, 36, 48, 72, 96 and 144
- Rate of BCR::ABL1 $\leq 10\%$ and $\leq 1\%$ at Weeks 12, 24, 36 and 48
- Rate of BCR::ABL1 $\leq 10\%$, BCR::ABL1 $\leq 1\%$, MMR, MR4 and MR4.5 by all-time points

Frequency and percentage of all molecular response categories (defined in [Appendix](#)) using FAS or FAS 2 will be presented for each time point.

For each endpoint above, the rate and the associated 95% confidence interval based on the Clopper-Pearson method will be presented. For the at-time-points summary, subjects discontinuing the treatment prior to a specific time point due to any reason or subjects without an available assessment at that time point will be considered as non-responders for that time point. For the by-time-points summary, subjects without any documented response for which an evaluable response assessment was never provided will be considered as non-responders for the period of time up to that time point.

The cumulative incidence of MMR will be graphically displayed by an increasing step function. This curve will increase each time (after randomization) at which a new responder is observed and thus will increase up to the best observed response rate (e.g. up to 50% if half of the subjects in the analysis population are able to achieve response).

Additional chromosomal abnormalities and occurrence of high-risk ACAs

The number and percentage of subjects achieving MMR at week 48 and week 96, and CCyR at week 48 will be presented by ACA status at baseline. Per NCCN 2024 guideline and ELN 2020 guideline, the major route ACA/Ph+ including trisomy 8, isochromosome 17q, second Ph, trisomy 19, and chromosome 3 abnormalities are considered as presence of ACA at baseline.

Time to MMR

Time to MMR is defined in protocol Section 8.3.1.1 and calculated as: date of first documented MMR - date of randomization +1. Descriptive statistics (minimum, maximum, median, quartiles, mean, SD) of time to MMR will be provided.

The FAS will be also used to perform similar Time-to-Event analyses as described below for duration of MMR.

For subjects in the FAS who have not experienced any MMR, the time will be censored as follows in the Kaplan-Meier analysis:

- If a subject does not achieve the specified response before the cut-off date for the analysis, censoring time will be the last molecular assessment (PCR) date on treatment prior to the cut-off date or the EoT visit, whichever comes first.
- If a subject discontinues study treatment prior to achieving a response for a reason other than disease progression or death, then the subject will be censored at the last molecular assessment (PCR) date on treatment prior to the cut-off date or the EoT visit, whichever comes first.
- If a subject discontinues study treatment prior to achieving a response due to progression or death, then the censoring time will be set to the longest follow-up time in the treatment group, that is, consider the response is impossible to reach.
- In case no on-treatment response assessment was performed, the subject will be censored at day 1.

The estimated cumulative incidence rates and 95% confidence intervals at 12, 24, 48, 72, 96 and 144 weeks will be presented. The cumulative incidence curve will be plotted.

Duration of MMR

Duration of MMR is defined in protocol Section 8.3.1.1 as the time from the date of first documented MMR to the earliest date of confirmed loss of MMR, progression to AP or BC, or CML-related death. The time will be censored at the last molecular assessment (PCR) date while on treatment for subjects who have not experienced any of the above events. The duration of MMR will be analyzed for the subjects in FAS who achieve MMR at any time.

Duration of MMR will be analyzed by K-M method and presented by K-M plots. The survival distribution of duration of MMR will be estimated using the Kaplan-Meier method, and Kaplan-Meier curves, medians and 95% confidence intervals [[Brookmeyer and Crowley 1982](#)] of the medians, along with the proportion of subjects who are still in MMR at 24, 48, 72, 96 and 144 weeks and the associated 95% confidence intervals, will be presented.

Duration of MR4 without loss of MMR will be analyzed in a similar fashion to the analysis of duration of MMR.

The additional subjects who were intolerant to the last TKI and were in MMR already at baseline will be assessed for the duration of MMR using FAS 2.

CCyR rates at time points

Subjects in FAS will be categorized with counts and percentages provided for cytogenetic response at week 48 and EOT. Shift tables will also be employed to examine the changes in cytogenetic response category from baseline.

CCyR rates at Weeks 48 and EOT and the associated 95% confidence intervals based on the Clopper-Pearson method will be presented.

TTF, PFS and OS

For each endpoint the survival distribution will be estimated using the Kaplan-Meier method, and Kaplan-Meier curves, medians and 95% confidence intervals [[Brookmeyer and Crowley](#)

[1982](#)] of the medians, along with the proportion of subjects who have not experienced the respective events at 1, 2 and 3 years and the associated 95% confidence intervals, will be presented.

TTF: For subjects in the FAS who have not reached treatment failure, their TTFs will be censored at the time of their last study assessment (PCR, cytogenetic, hematologic or extramedullary) before the cut-off date.

PFS: For subjects who have not experienced an event (disease progression to AP/BC or death from any cause), their PFS times will be censored at the date of last study assessment (PCR, cytogenetic, hematologic or extramedullary) before the cut-off date.

OS: Subjects who are alive at the time of the analysis data cutoff date will be censored at the date of last contact (see [Section 2.1.1](#)) before the cut-off date.

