9.1 Discontinuation from study treatment and from study

9.1.1 Discontinuation from study treatment

Discontinuation of study treatment for a participant occurs when study treatment is permanently stopped for any reason (earlier than the planned completion of study drug administration) and can be initiated by either the participant or the investigator.

The investigator must discontinue study treatment for a given participant if, he/she believes that continuation would negatively impact the participant's well-being.

Study treatment must be discontinued under the following circumstances:

- Participant/guardian decision
- Pregnancy
- Use of prohibited treatment. Refer to [Section 6.2.2](#).
- Any situation in which continued study participation might result in a safety risk to the participant
- In the case of certain adverse events and re-occurrence of adverse events (see [Table 6-4](#))
- Major Protocol Deviation, or any other protocol deviation that results in a significant risk to the patient's safety.

In addition to the general discontinuation criteria, the following study specific criteria will also require discontinuation of study treatment:

- In the event of treatment failure the patient should be discontinued from the study treatment. The ELN criteria 2020 do not make provisions for treatment failure in 3rd line however they define that a level of BCR-ABL1 > 1% IS and failure to achieve CCyR is not sufficient for optimal survival. The following events will constitute 'treatment failure':
 - BCR-ABL1 >1% IS at 48 weeks after initiation of therapy or no complete cytogenetic response at 48 weeks.

- Patients fulfilling treatment failure criteria above but without alternative treatment options may however be continued on study drug if in the investigators opinion they are obtaining benefit from the drug. Patients with BCR-ABL 1 greater than 10% after 48 weeks of treatment or patients with signs of progression to AP and BC must however be discontinued.
- Patients with newly emerging T315I mutation and lack or loss of response. While asciminib has known activity against CML with additional T315I mutation, the recommended dose of 200 mg BID for the treatment of T315I is not in use in the study. In case a patient demonstrates a new T315I mutation on asciminib, patients should not continue in the study.

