1. ***pre-treatment period:*** from day of subject’s informed consent to the day before first administration of study treatment
2. ***on-treatment period:*** from date of first administration of study treatment to 30 days after date of last administration of study treatment (including start and stop date).
3. ***post-treatment period:*** starting at day 31 after last administration of study treatment.

If dates are incomplete in a way that clear assignment to pre-, on-, post-treatment period cannot be made, then the respective data will be assigned to the on-treatment period.

Safety summaries (tables, figures) on the corresponding Safety set include only data from the on-treatment period with the exception of baseline data which will also be summarized where appropriate (e.g. change from baseline summaries). In particular, summary tables for adverse events (AEs) will summarize only on-treatment events, with a start date during the on-treatment period. In addition, a separate summary for death will be provided.

However, all safety data (including those from the pre-treatment and post-treatment) will be listed and flagged as appropriate.

Efficacy summaries on the FAS and FAS 2 (apart from OS and PFS) include data from baseline up to either the last assessment on or before the End of Treatment (EoT) visit or before or on treatment failure, whichever is the earliest.

The efficacy assessments collected post-treatment failure or post-EoT visit are not included in any efficacy analyses (except for OS and PFS analyses). However, they will be listed and flagged as appropriate.

Windows for multiple assessments

Data such as molecular response, cytogenetic response collected over time (including unscheduled visits) will be summarized by scheduled time point. As subjects do not always adhere to the visit schedule, visits will be remapped according to visit windows defined in Tables 2-1 to Table 2-3 of this document to enable by-visit analysis. Only those protocol-defined visits will have the visit window defined. Each assessment (including the end of treatment assessment), either scheduled or unscheduled, will have a mapped visit assigned, as long as study day is available, according to the defined visit window up to the date with data included.

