2.5.2 Statistical hypothesis, model, and method of analysis

The primary estimand will be analyzed based on the data from the FAS and according to the Intention-To-Treat (ITT) principle. Exact test for single proportion will be used at the one-sided 2.5% level of significance.

The null hypothesis is that the MMR rate at Week 48 is equal to 0.23. The alternative hypothesis is that the rate is greater than 0.23.

$H_0: \pi=0.23$ vs. $H_1: \pi >0.23$

where π is the major molecular response (BCR::ABL1 \leq 0.1% IS) rate at Week 48. MMR rate and its 95% confidence interval based on the Clopper-Pearson method will also be presented.

The null hypothesis will be rejected when the lower bound of the two-sided 95% CI is above 23%.

Summary statistics of MMR at week 48 will also be presented by randomized groups.

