2.13 Interim analysis

No formal interim analysis is planned for this trial. The following analyses are planned as detailed below.

- 48-week primary analysis: Formal testing of the primary endpoint will be performed. Analyses of other efficacy endpoints at and by week 48 and safety analyses will also be performed.
- 96-week analysis: Analyses of efficacy endpoints at and by week 96 and safety analyses will be performed.
- End of study treatment analysis similar to the 96-week analysis without formal statistical testing. All efficacy and safety analyses will be included.

3 Sample size calculation

A sample size of 156 subjects (randomized to either asciminib 40 mg b.i.d. or 80 mg q.d.) will have 80% power to reject the null hypothesis proportion of 23% (upper limit of 95% exact binomial CI of the MMR rate at Week 48 in Bosutinib arm in ASCEMBL: see below) at 0.025 one-sided level of significance if the true rate (under alternative hypothesis) is 33% (considering a clinically meaningful difference of 10% or more) using exact test for single proportion (nQuery 7).

The MMR rate (95% CI) at Week 48 in Bosutinib arm of ASCEMBL trial (at ASCEMBL study Week 24 primary CSR (Data cut-off date of 25-May-2020, Table 14.2-1.1.1)) was 11.1 % (4.2% – 22.6%); 54 subjects were eligible for this sample size computation.

An additional 30 subjects based on medical justification (randomized to either asciminib 40 mg b.i.d. or 80 mg q.d.) intolerant only to last TKI and in MMR at baseline will also be analyzed.

4 Change to protocol specified analyses

Not applicable.

5 Appendix

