5.5 Derivation of response rates and categories

5.5.1 Response rate at a specific time point

The molecular and cytogenetic response evaluations will be summarized by the following mutually exclusive categories which are based on the respective assessment within the time window:

- **Response categories** (sections 5.4.1 and 5.4.2): Subjects with an available assessment at that time point (+/- time window) indicating any of the response categories.
- **No response:** Subjects with assessment at that time point (+/- time window) indicating 'no response'
- **Missing:** Subjects without an evaluable response assessment at that time point (+/- time window). This category is then further split into subjects who are ongoing without treatment failure at the beginning of the relevant time window, subjects who are ongoing with treatment failure at the beginning of the relevant time window, subjects who discontinued due to lack of efficacy, disease progression (PD) or death and subjects who discontinued due to other reasons.

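### The time-to-MMR analysis censors patients who stop for lack of efficacy or treatment failure, so its cumulative incidence estimates are too high from the first such stop onward

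*SAP*

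**What the plan says.** Time to MMR is a named secondary objective for patients not in MMR at baseline. SAP 2.6.2 (Time to MMR) adds a time-to-event analysis on the FAS, with cumulative incidence estimates and 95% confidence intervals at Weeks 12, 24, 48, 72, 96 and 144.

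Subjects without MMR who stop treatment are handled in two ways:

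- Stop due to progression or death: the time is set to the longest follow-up in the group, because MMR is then regarded as out of reach.
- Stop "for a reason other than disease progression or death, then the subject will be censored at the last molecular assessment (PCR) date on treatment" (or at the EoT visit or cut-off, if sooner).

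Other sections bear on who falls in the second group:

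- SAP 5.4.7 defines progression as accelerated phase, blast crisis or CML-related death. Lack of efficacy is not included.
- Protocol 9.1.1 states: "In the event of treatment failure the patient should be discontinued from the study treatment". Failure there means BCR-ABL1 above 1% or no CCyR at Week 48, with an exception for some patients without alternatives. SAP 5.4.4 has the same criterion and adds others.
- SAP 5.5.1 splits missing assessments differently from 2.6.2. Among those who stopped, it separates "subjects who discontinued due to lack of efficacy, disease progression (PD) or death and subjects who discontinued due to other reasons".
- The at-time-point rule in SAP 2.6.2 scores "subjects discontinuing the treatment prior to a specific time point due to any reason" as non-responders.
- SAP 2.1.1 runs efficacy summaries "up to either the last assessment on or before the End of Treatment (EoT) visit or before or on treatment failure", whichever is earliest.
- SAP 5.6.2 says cumulative incidence will be estimated by competing-risk analysis, with code 0 for censored subjects and another code for drop-out due to a competing risk. It does not list the competing risks.

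**The concern.** Kaplan-Meier gives each censored subject the later MMR chance of those still under observation. That is reasonable for a stop unrelated to response, such as moving away. It is not reasonable for a patient who leaves because BCR::ABL1 is above 1%, CCyR is absent or the drug is judged not to be working. Those who remain have been selected for better response.

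The SAP sees this for progression and death but not for the commoner efficacy-related stops, although its own 5.5.1 puts all three together. The result would be a time-to-MMR cumulative incidence, with confidence limits, that overstates how many patients reach MMR on asciminib. It would also exceed the step-function curve in the same section, which ends at the observed response rate, so the report would carry two different figures for cumulative MMR.

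**Working it through.** **The plan's own figure.** The SAP states no expected value for time to MMR. Its one design figure is for the primary test: "Exact test for single proportion will be used at the one-sided 2.5% level of significance", against a null MMR rate of 0.23 (SAP 2.5.2), and 80% power with 156 subjects "if the true rate (under alternative hypothesis) is 33" per cent (SAP Section 3). This reproduces: the smallest count r with P(X ≥ r | 0.23) ≤ 0.025 is 47 of 156, with exact size 0.0241 and power 80.1%. It serves here only to set a Week 48 level of 51/156 = 32.7%, close to the design alternative.

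**Step 1: the excess in closed form.** Let m be the proportion in MMR by Week 48, l the proportion of all patients who stop at Week 48 for lack of efficacy without MMR, and h the chance of later MMR by Week 96 among those remaining. Assume no other censoring.

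- Stops censored: 1 − (1 − m)(1 − h) = m + (1 − m)h
- Stops kept at risk, as for progression and death: m + (1 − m − l)h
- Difference: l × h

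The excess does not depend on m. If the stopped patients would have had some later chance h′ had they stayed on, it is l(h − h′), still upward whenever h′ < h.

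**Step 2: numbers.** The value l = 0.21 carries over the 21.0% lack-of-efficacy discontinuation on asciminib quoted in protocol 1.1. The lower value of l, and m and h, are assumptions. With m = 0.40, l = 0.21, h = 0.25:

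- Censored: 1 − 0.60 × 0.75 = 55.0%
- Kept at risk: 0.40 + 0.39 × 0.25 = 49.8%
- Excess: 0.21 × 0.25 = 5.25 points

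| Excess at Week 96 (points) | h = 0.15 | h = 0.25 | h = 0.35 |
|---|---|---|---|
| l = 0.10 | 1.50 | 2.50 | 3.50 |
| l = 0.21 | 3.15 | 5.25 | 7.35 |

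**Step 3: visit by visit on 156 patients.** Take 51 in MMR by Week 48, 33 lack-of-efficacy stops (21%) and no other censoring. New first MMRs (8, 16 or 23 patients) are spread over Weeks 60 to 144.

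One case by hand, with all 33 stops at Week 48 and 16 later MMRs, 8 of them by Week 96. The number left at risk is 156 − 51 − 33 = 72.

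- Censored: 1 − (105/156)(64/72) = 40.2%
- Kept at risk: (51 + 8)/156 = 37.8%

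The ranges below reflect when the 33 stops fall.

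| Later first MMRs | Week 96, kept at risk | Week 96, censored | Week 144, kept at risk | Week 144, censored |
|---|---|---|---|---|
| 5% (8) | 35.3% | 36.4-41.0% | 37.8% | 40.2-44.4% |
| 10% (16) | 37.8% | 40.2-44.4% | 43.0% | 47.7-51.4% |
| 15% (23) | 40.4% | 43.9-47.9% | 47.4% | 53.8-57.5% |

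The excess is 1.2 to 7.5 points at Week 96 and 2.4 to 10.0 points at Week 144, upward in every scenario.

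**Step 4: stops before Week 48.** If all 33 stops fall before Week 48, the Week 48 estimate is already 37.5% instead of 32.7%, an excess of 4.8 points.

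**Step 5: more removals at Week 48.** With 16 later MMRs and 20%, 30% or 40% of patients (31, 47 or 62) removed at Week 48, the Week 144 estimate is 47.3%, 51.3% or 57.7% against 43.0%.

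**The case against.** The strongest objection is SAP 5.6.2. The Week 12 to 144 figures are labelled cumulative incidence, and that section says cumulative incidence comes from a competing-risk analysis. If lack-of-efficacy and failure stops were coded as competing events, the bias would go. But 5.6.2 names no competing event, and 2.6.2, the only text that classifies these stops, says they are censored, which is code 0. A competing-risk estimator with these subjects coded 0 keeps the bias; with no progression or death it equals one minus Kaplan-Meier.

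The second objection is that little rides on this, and that stands. No secondary efficacy endpoint is tested, protocol 12.5.1 planned only descriptive statistics for time to MMR, and unbiased figures will appear in the same report.

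The third is that the size is conjecture, and that stands too. The 40% and the 15-35% have no source in the documents. The 21.0% accrued over a median follow-up of 14.9 months in patients selected on ELN 2013 failure criteria, whereas this trial expects less advanced disease. The sentence in protocol 1.1 could also be read as a share of discontinuations: 0.376 × 0.210 = 7.9% of patients, giving 0.079 × 0.15 = 1.2 to 0.079 × 0.35 = 2.8 points. None of this changes the direction.

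A reader might infer more than the documents support:

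- **That every cumulative MMR figure is biased.** The by-time-point rates keep non-responders in the denominator, and the step function rises only to the observed rate.
- **That the bias starts only after Week 48.** It starts with the first efficacy-related stop.
- **That the censoring rule alone pools efficacy stops with unrelated ones.** The at-time-point rule also pools all reasons, but as non-responders, which cannot inflate a rate.
- **That patients who fail but stay on treatment certainly leave this analysis at Week 48.** SAP 2.1.1 points that way. But the first censoring bullet in 2.6.2 uses the last on-treatment PCR, and SAP 2.5.6 plans Week 96 and 144 MMR rates for dose-escalated subjects, who can include patients not in MMR at Week 48. The sections conflict.

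**Conclusion.** The point holds for the time-to-MMR analysis of SAP 2.6.2 and for nothing wider. Stops for lack of efficacy or treatment failure are classed as uninformative when they are not, and the resulting cumulative incidence is too high from the first such stop. The gap grows with follow-up and is plainest at Weeks 72, 96 and 144.

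The excess is l × h when the stops occur together at Week 48: about 1.5 to 7 points at Week 96 for l of 10-21% and h of 15-35%. It is larger by Week 144 in the visit-by-visit scenarios. This is illustrative, not a forecast, because the documents give neither the number nor the timing of such stops in this trial.

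The primary conclusion is untouched, since SAP 2.5.3 scores any discontinuation before Week 48 as non-response. The correction is still worth making: the estimates are planned outputs for a named secondary objective, the bias favours the drug, and the SAP already makes the right grouping in 5.5.1.

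**What to change.** 1. In SAP 2.6.2 (Time to MMR), extend the progression/death bullet to subjects without prior MMR who discontinue study treatment because of lack of efficacy or treatment failure. Keep censoring at the last PCR only for stops unrelated to efficacy.
2. In SAP 5.6.2, list the same events as the competing risks for time to MMR, so that 2.6.2, 5.5.1 and 5.6.2 agree.
3. For subjects who meet a failure criterion but stay on treatment, reconcile SAP 2.1.1 with 2.6.2 on whether their later PCRs count. Do not simply declare MMR unreachable for them. Protocol 9.1.1 and SAP 5.4.4 allow some to continue, and SAP 5.4.2 groups missing cytogenetic evaluations with non-response (unless the subject is in MMR), so a missing Week 48 marrow could trigger the label. That rule could bias the estimate downward.

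The cost is one bullet, a short list of events, a reconciling sentence and the matching programming. No new data are needed, because reasons for discontinuation are already collected. The downside for the sponsor is a slightly less favourable reported cumulative MMR.
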